## 8.2 Safety Assessments and Procedures

The safety profile of the study intervention will be assessed through the recording, reporting, and analysis of baseline medical conditions, AEs, physical examination findings, vital signs, electrocardiogram (ECGs), and laboratory tests.

Comprehensive assessment of any potential toxicity experienced by each participant will be conducted starting when the participants give informed consent and throughout the study. The Investigator will report any AEs, whether observed by the Investigator or reported by the participant; the reporting period is specified in Section 8.3.1 (Time Period and Frequency for Collecting Adverse Event and Serious Adverse Event Information).

The safety assessments will be performed according to the Schedule of Activities (Table 1). Periodic evaluations of the study data will be conducted by an IDMC to ensure safety and the validity and scientific merit of the study (see Section 8.2.4).

Ongoing events at the 12-week Safety Follow-up visit should continue to be monitored and documented until resolution or resolution with sequelae. All serious adverse events (SAEs) ongoing at the End-of-Treatment visit must be monitored and followed up by the Investigator until stabilization or until the outcome is known, unless the participant is documented as “lost to follow-up”. Reasonable attempts to obtain this information must be made and documented. It is also the responsibility of the Investigator to ensure that any necessary additional therapeutic measures and follow-up procedures are performed.

If a liver function test is elevated in an HBV- or HCV-positive participant, HBV DNA or HCV ribonucleic acid (RNA) must be monitored to exclude the possibility of reactivation of viral hepatitis. In case of viral reactivation, follow the HBV and HCV management guidelines.

### 8.2.1 Physical Examinations and Vital Signs

- Vital signs, physical examinations, and ECOG PS will be conducted at Screening and at subsequent visits as indicated in the Schedule of Activities ([Table 1](#)). These should be documented in the eCRF.
- A complete physical examination at Screening will include, at a minimum, assessments of the cardiovascular, respiratory, gastrointestinal, and neurological systems. Height (at Screening Visit only) and weight will also be measured and recorded.
- A brief physical examination (at all other scheduled visits other than Screening) will include, at a minimum, assessments of the skin, lungs, cardiovascular system, and abdomen (liver and spleen).
- Investigators should pay special attention to clinical signs related to previous serious illnesses.
- General status, such as asthenia or appetite, should be evaluated at Baseline, as these are usually affected. Pre-existing symptoms of underlying conditions and/or signs of infection should be investigated as clinically indicated.
- Abnormal findings are to be reassessed at subsequent visits.
- Vital signs including heart rate, body temperature, pulse rate, respiratory rate, and blood pressure will be assessed and recorded in the eCRF.
- Blood pressure and pulse measurements will be assessed with a completely automated device. Manual techniques will be used only if an automated device is not available.
- Blood pressure and pulse measurements should be preceded by at least 5 minutes of rest for the participant in a quiet setting without distractions (e.g., television, cell phones).
- Vital signs will be measured in a semi-supine position after 5 minutes rest and will include temperature, systolic and diastolic blood pressure, pulse and respiratory rate.
- Blood oxygen saturation will be measured with a pulse oximeter and recorded in the eCRF.

### 8.2.2 Electrocardiograms

Single 12-lead ECGs will be obtained as outlined in the Schedule of Activities ([Table 1](#)) using an ECG machine that automatically calculates the heart rate and measures PR, QRS, QT, and QTc intervals.

### 8.2.3 Clinical Safety Laboratory Assessments

- Blood and urine samples will be collected for the clinical laboratory tests listed in [Appendix 5](#) at the time points listed in the Schedule of Activities ([Table 1](#)). All samples should be clearly identified.
- Additional tests may be performed at any time during the study, as determined necessary by the Investigator or required by local regulations.
- The tests will be performed by the local laboratory.

- The Sponsor will receive a list of the local laboratory normal ranges before shipment of study intervention. Any changes to the ranges during the study will be forwarded to the Sponsor or designated organization.
- The Investigator will review each laboratory report, document their review, and record any clinically relevant changes occurring during the study in the AE section of the eCRF. The laboratory reports must be filed with the source documents.
- If a participant has a clinically significant abnormal laboratory test value that is not present at Baseline, the test should be closely monitored until the test value has returned to the normal range or the Investigator has determined that the abnormality is chronic or stable.
- The report of the results must be retained as a part of the participant's medical record or source documents.
- Serum KL-6, SP-A, and SP-D levels will be measured at sites in Japan for potential early detection of pneumonitis. Inclusion of these markers are for indicating potential lung-related toxicity only; further investigations, like chest CT, etc., will be performed for a confirmatory diagnosis.
- Pregnancy testing (serum or highly sensitive urine test, as required by local regulations) will be conducted at monthly intervals during study intervention administration and at the time points specified in the Schedule of Activities ([Table 1](#)), including at the end of relevant systemic exposure of the study intervention.

## 8.2.4 Review Committees

The following committees will be involved in the study: IDMC, IRC, and Study Steering Committee.

### Independent Data Monitoring Committee (IDMC)

To ensure participants' safety during the study, an external IDMC will periodically review safety data. The IDMC will be composed of a minimum of 3 voting members, including an independent biostatistician, and 2 independent oncologists (BTC experts). The full details on membership, mandate, and processes of the IDMC are outlined in the IDMC charter.

### Independent Radiology (Review) Committee (IRC)

The IRC will be composed of a minimum of 3 members. The role of the IRC will be to review radiographic image findings, physical findings, and other clinical data for the determination of the best overall response (OR) and date of disease progression for each participant. The full membership, mandate, and processes of the IRC will be detailed in the IRC charter.

## 8.3 Adverse Events and Serious Adverse Events

The definitions of an AE and a SAE are in [Appendix 4](#).

### **8.3.1 Time Period and Frequency for Collecting Adverse Event and Serious Adverse Event Information**

The AE reporting period for safety surveillance begins when the participant is initially included in the study (date of first signature of informed consent/date of first signature of first informed consent) and continues until the 28-day Safety Follow-up visit, defined as 28 days ( $\pm$  5 days) after the last study intervention administration. After this visit, all SAEs and non-serious treatment-related AEs should be documented until the last Safety Follow-up visit, defined as 12 weeks ( $\pm$  2 weeks) after the last study intervention. Ongoing events at the 12-week Safety Follow-up visit should continue to be monitored and documented until resolution or resolution with sequelae, unless the participant is documented as “lost to follow-up”.

Any SAE assessed as related to study intervention must be recorded and reported, as indicated in [Appendix 4](#), whenever it occurs, irrespective of the time elapsed since the last administration of study intervention.

The method of recording, evaluating, and assessing causality of AEs (including SAEs) and the procedures for completing and transmitting SAE reports are in [Appendix 4](#).

### **8.3.2 Method of Detecting Adverse Events and Serious Adverse Events**

At each study visit, the participant will be queried on changes in his or her condition. During the reporting period, any unfavorable changes in the participant’s condition will be recorded as AEs, regardless if reported by the participant or observed by the Investigator.

Complete, accurate, and consistent data on all AEs experienced for the duration of the reporting period (defined below) will be reported on an ongoing basis in the appropriate section of the eCRF. All SAEs must be additionally documented and reported using the appropriate SAE Report Form as specified in [Appendix 4](#).

### **8.3.3 Follow-up of Adverse Events and Serious Adverse Events**

Adverse events are recorded and assessed continuously throughout the study, as specified in Section 8.3.1 (Time Period and Frequency for Collecting Adverse Event and Serious Adverse Event Information) and are assessed for their outcome at the 28-day Safety Follow-up visit.

All SAEs ongoing at the 28-day Safety Follow-up visit must be monitored and followed up by the Investigator until stabilization or until the outcome is known, unless the participant is documented as “lost to follow-up.” Reasonable attempts to obtain this information must be made and documented. It is also the responsibility of the Investigator to ensure that any necessary additional therapeutic measures and follow-up procedures are performed. Further information on follow-up procedures is given in [Appendix 4](#) (Adverse Events: Definitions and Procedures for Recording, Evaluating, Follow-up, and Reports).

### **8.3.4 Regulatory Reporting Requirements for Serious Adverse Events**

The Sponsor will send appropriate safety notifications to Health Authorities in accordance with applicable laws and regulations.

The Investigator must report SAEs (particularly deaths) in accordance with applicable site-specific requirements to the Institutional Review Board (IRB) that approved the study.

In accordance with International Council for Harmonisation (ICH) Good Clinical Practice (GCP) and the Japanese ministerial ordinance on GCP, the Sponsor/designee will immediately inform all the study Investigators and the Heads of the study sites of findings that could adversely affect the safety of participants, impact the conduct of the study, or alter the IRB's approval/favorable opinion to continue the study. In line with respective applicable regulations, the Sponsor/designee will immediately inform all the study Investigators and the Heads of the study sites of AEs that are both serious and unexpected and considered to be related to the administered product ("suspected unexpected serious adverse reactions" or SUSARs). In addition, per applicable regulations, the Sponsor/designee will inform the study Investigators and the Heads of the study sites of all SAEs that were reported to the Health Authorities. In accordance with the Japanese regulatory requirements concerning safety reporting, the Investigator should place copies of the Safety Reports in the Investigator Site File. The Head of the study site should also maintain copies of Safety Reports appropriately.

When specifically required by regulations and guidelines, the Sponsor/designee will provide appropriate Safety Reports directly to the concerned lead Independent Ethic Committee (IEC)/IRB and will maintain records of these notifications. When direct reporting is not clearly defined by national or site-specific regulations, the Investigator will be responsible for promptly notifying the concerned IEC/IRB of any Safety Reports provided by the Sponsor/designee and of filing copies of all related correspondence in the Investigator Site File.

For studies covered by the European Directive 2001/20/EC, the Sponsor's responsibilities regarding the reporting of SAEs/SUSARs/Safety Issues will be carried out in accordance with that Directive and with the related Detailed Guidance documents.

### **8.3.5 Pregnancy**

Only pregnancies the Investigator considers to be related to the study intervention (e.g., resulting from a drug interaction with a contraceptive method) are AEs. However, all pregnancies with an estimated conception date during the period defined in Section 8.3.1 (Time Period and Frequency for Collecting Adverse Event and Serious Adverse Event Information) must be recorded in the AE page/section of the eCRF for both pregnancies in female participants and pregnancies in female partners of male participants. The Investigator must notify the Sponsor/designee in an expedited manner of any pregnancy using the Pregnancy Report Form, which must be transmitted by the same process specified for SAE reporting in [Appendix 4](#), section on Reporting Serious Adverse Events.

Investigators must actively follow-up, document, and report on the outcome of all these pregnancies, even if the participants are withdrawn from the study.

The Investigator must notify the Sponsor/designee of these outcomes using the Pregnancy Report Form. If an abnormal outcome occurs, the SAE Report Form will be used if the participant sustains an event and the Parent-Child/Fetus Adverse Event Report Form if the child/fetus sustains an event. Any abnormal outcome (e.g., spontaneous abortion, fetal death, stillbirth, congenital anomalies, ectopic pregnancy) must be reported in an expedited manner, as specified in Section 8.3.1, while normal outcomes must be reported within 45 days after delivery.

In the event of a pregnancy in a participant occurring during the study, the participant must be discontinued from study intervention. The Sponsor/designee must be notified without delay and the participant must be followed as indicated above.

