## Sex

14. Male participants are eligible to participate if they agree to the following during the intervention period and for at least 4 months after the last dose of study intervention:
  - Refrain from donating spermPLUS, either

- Abstain from intercourse with a female
- OR
- Use a male condom:
  - When having sexual intercourse with a woman of childbearing potential (WOCBP), who is not currently pregnant, **and** advise her to use a highly effective contraceptive method with a failure rate of < 1% per year, as described in [Appendix 3](#), since a condom may break or leak
  - When engaging in any activity that allows for exposure to ejaculate.

15. A female is eligible if she is not pregnant or breastfeeding, and at least one of the following conditions applies:

- Not a WOCBP
- OR
- If a WOCBP, use a highly effective contraceptive method (i.e., with a failure rate of < 1% per year), preferably with low user dependency, as described in [Appendix 3](#) for the following time periods:
  - Before the first dose of the study intervention, if using hormonal contraception:
    - Has completed at least one 4-week cycle of an oral contraception pill and either had or has begun her menses
  - OR
  - Has used a depot contraceptive or extended-cycle oral contraceptive for least 28 days and has a documented negative pregnancy test using a highly sensitive assay.
- During the intervention period
- After the study intervention period (i.e., after the last dose of study intervention is administered) for at least 2 months after the last dose of study intervention.

The Investigator evaluates the effectiveness of the contraceptive method in relationship to the first dose of study intervention.

- Have a negative serum or highly sensitive urine pregnancy test, as required by local regulations, within 24 hours before the first dose of study intervention. If a urine test cannot be confirmed as negative (e.g., an ambiguous result), a serum pregnancy test is required.
- Additional requirements for pregnancy testing during and after study intervention are in [Section 8.2.3](#).
- The Investigator reviews the medical history, menstrual history, and recent sexual activity to decrease the risk for inclusion of a female with an early undetected pregnancy.

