### **6.9.6.2                    Embryofetal Toxicity**

Embryofetal toxicities are a known risk of the PD-1/PD-L1 targeting class and are considered important potential risks for M7824. Animal models link the PD-1/PD-L1 signaling pathway with maintenance of pregnancy through induction of maternal immune tolerance to fetal tissue. Embryofetal toxicity is an important potential risk of M7824. An appropriate contraception warning is provided as part of the inclusion criteria. Pregnant and breastfeeding women are not allowed in the M7824 study, and adequate contraceptive measures are recommended during the study to minimize or eliminate the potential risk to the developing fetus.

Respective safety measures comprise inclusion/exclusion criteria for participation in clinical studies with M7824, guidance for prevention, monitoring, and medical management of potential risks, as well as guidance on study intervention interruption or discontinuation.

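### Mandatory recording of partner pregnancies ends about 38 days (24 to 52) before the protocol's own male contraception period does, and it is unclear whether notification and follow-up fill the gap

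*Protocol*

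**What the plan says.** **Recording.** Protocol Section 8.3.5 treats a pregnancy as an adverse event only if the investigator considers it related to study intervention. Separately, it requires entry on the adverse event page of the eCRF of "all pregnancies with an estimated conception date during the period defined in Section 8.3.1", and states that this holds "for both pregnancies in female participants and pregnancies in female partners of male participants". Partners have no window of their own.

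**The period referred to.** Section 8.3.1 starts at informed consent and contains two endpoints. The general adverse event reporting period "continues until the 28-day Safety Follow-up visit, defined as 28 days" (±5 days) after the last administration. After that visit, "all SAEs and non-serious treatment-related AEs should be documented until the last Safety Follow-up visit, defined as 12 weeks" (±2 weeks) after the last administration. Section 8.3.5 does not say which endpoint governs pregnancies.

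**Contraception.** In Section 5.1, criterion 14 applies the male measures "during the intervention period and for at least 4 months after the last dose of study intervention". Criterion 15 applies the female measures "for at least 2 months after the last dose of study intervention".

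**Why it is collected.** Section 6.9.6.2 states: "Embryofetal toxicity is an important potential risk of M7824". It also points to the contraception wording in the inclusion criteria as part of managing that risk.

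**Notification and follow-up.** After the recording sentence, Section 8.3.5 requires rapid sponsor notification on the Pregnancy Report Form. That sentence refers to pregnancies generally and repeats no window. The next paragraph requires active follow-up of the outcome of these pregnancies, including after withdrawal from the study.

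**The concern.** The protocol sets one period after the last dose in which conception by a male participant's partner is to be avoided, and a shorter one in which such a conception must be recorded. Section 8.3.5 borrows its window from adverse event collection, which was not built around contraception. A partner pregnancy conceived in week 15 falls inside the 4-month contraception period but after the latest possible 12-week visit, at week 14.

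At stake is the completeness of the pregnancy information for a risk that the protocol itself names. The documents contain no other collection rule for partner pregnancies. If sites read the section differently, some will report late conceptions and others will not, so the number of pregnancies reported cannot be read as a complete count for the contraception period.

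**Working it through.** **Inputs**

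- Male contraception period: at least 4 months after the last dose (Protocol Section 5.1, criterion 14).
- Female contraception period: at least 2 months after the last dose (criterion 15).
- End of the Section 8.3.1 period, longer reading: 12 weeks ± 2 weeks, so 70, 84 or 98 days.
- End of the Section 8.3.1 period, shorter reading: 28 ± 5 days, so 33 days at the latest.
- Month length: 30.4375 days (SAP Section 9, conversion factors). The SAP sets this for analysis; using it here is an assumption.

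The plan states no figure of its own to reproduce. The check is a comparison of durations.

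**Partners of male participants**

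4 × 30.4375 = 121.75 days. Gap = 121.75 minus the end of the recording window.

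| End of recording window | Day after last dose | Gap in days | Gap in weeks |
|---|---|---|---|
| 12-week visit, nominal | 84 | 37.75 | 5.4 |
| 12-week visit, latest | 98 | 23.75 | 3.4 |
| 12-week visit, earliest | 70 | 51.75 | 7.4 |
| 28-day visit, nominal | 28 | 93.75 | 13.4 |
| 28-day visit, latest | 33 | 88.75 | 12.7 |

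**Sensitivity to month length.** With months of 28 to 31 days, 4 months is 112 to 124 days. The gap to week 12 is then 28 to 40 days, and to week 14 it is 14 to 26 days. It is positive in every case.

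**Female participants**

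2 × 30.4375 = 60.875 days. This lies inside even the earliest 12-week visit (70 days), so there is no gap on the longer reading. On the 28-day reading the shortfall would be 60.875 − 28 = 32.875 days.

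**Can an existing contact cover the gap?** Section 4.1 schedules Long-term Follow-up every 12 weeks after Safety Follow-up, so the first falls nominally 12 + 12 = 24 weeks (168 days) after the last dose. If both contacts are 2 weeks early, it falls at 10 + 10 = 20 weeks (140 days). That is still 140 − 121.75 = 18.25 days after the 4-month point, so one contact can ask about the whole 4 months.

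**The case against.** The strongest counter-argument is that late partner pregnancies would still reach the sponsor. The window limits the eCRF entry. The notification sentence carries no window, and the follow-up duty can be read as attaching to whatever has been notified. Related serious adverse events are reportable at any time under Section 8.3.1, and Appendix 4 lists congenital anomaly as a seriousness criterion. A reader might infer that late conceptions are lost and their outcomes never sought; the documents do not support that. What remains is uncertainty. The notification sentence comes directly after the window-limited rule and may be read within it. The serious-event route covers only serious outcomes judged related, so it would not capture a normal pregnancy.

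A reader might also infer that female participants lose their second month. That holds only if the 28-day endpoint applies, and this reading fits less well. Section 8.3.5 cites the whole of Section 8.3.1, including its serious-event part, and sends the pregnancy form through the serious-event process. The Schedule of Activities also appears to place a pregnancy test at the 12-week follow-up, although its columns are hard to read in the extracted text. For female participants an unnamed endpoint needs naming; a gap is not established.

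Finally, Section 6.9.6.2 describes a maternal mechanism, and nothing in the documents describes fetal exposure through a male participant. It would go too far to call these pregnancies exposures. They are conceptions inside a period in which the protocol itself asks men to take precautions. The objection that events will be rare also stands, and it limits the weight of the point.

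**Conclusion.** The mismatch is real on every reading of Section 8.3.1. Taking the longer endpoint, mandatory eCRF recording of partner pregnancies stops about 38 days before the protocol's own minimum male contraception period ends, with a range of 24 to 52 days across the 12-week visit window. No other section closes the gap, and the text leaves open whether notification and outcome follow-up extend beyond the recording window.

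The size rests on the 12-week endpoint being the one intended and on the SAP's month length. Criterion 14 sets a minimum, so these figures describe the shortest contraception period it allows. The documents give no expected number of partner pregnancies; that few will occur is an assumption. This is a modest point about safety data. It implies no view on which contraception duration is correct.

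**What to change.** Reconcile Section 5.1 (criteria 14 and 15), Section 8.3.1 and Section 8.3.5 by stating an explicit conception window in Section 8.3.5, and say that the same window governs eCRF recording, notification on the Pregnancy Report Form and outcome follow-up.

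- **Start:** keep informed consent. A start at first dose would drop conceptions during Screening that are covered now.
- **End, partners of male participants:** no earlier than the end of the protocol's own male contraception period.
- **End, female participants:** state that the 12-week endpoint applies and not the 28-day visit.

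Ask male participants about partner pregnancy at the first scheduled Long-term Follow-up. The protocol allows that contact to be a chart review, which may not show a partner's pregnancy, so in that case it should be made by telephone.

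The cost is a short protocol text change, one added question, and a telephone call in place of a chart review for some male participants. No visit or procedure is added. The yield is likely to be small.
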